#### **METHODS**

#### **General Study Design**

This is a single center, open label, pragmatic, non-inferiority, cluster randomized controlled trial. Patients with a PPL requiring navigational bronchoscopic sampling will be included. We have one EMN platform and one SSCB platform at VUMC. The platform set up in each of our two operating rooms will be randomly allocated each morning. Any navigational bronchoscopy scheduled in a given operating room that day will be performed with the platform allocated to that room on that day.

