# STATISTICAL CONSIDERATIONS

## Sample Size Calculation

EMN diagnostic yield varies widely in the literature (1). Based on data from prior studies and our own published data, we estimated the diagnostic yield of EMN to be 80% (10, 12). The diagnostic yield of SSCB has not been fully elucidated, but published data suggest an overall diagnostic yield of 80% as well (5,7). Assuming the diagnostic yield for EMN is 80%, with a non-inferiority margin set at 10%, cluster size of 2, and no intracluster correlation, we need 202 clusters (OR-days) to have an 80% power to conclude noninferiority at a one-sided type I error rate of 5%, which corresponds to a target of 425 subjects to reach 202 per arm. The noninferiority margin has been chosen based on what would be considered a clinically significant difference (or, put differently, a difference which might influence a hospital to purchase one platform over the other). In case our average cluster size does not reach 2, we will plan to increase the number of clusters to meet our target enrollment of 425 subjects to reach 202 per arm.

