## **Statistical Analysis Plan**

Standard consort diagram will be created. Descriptive statistics including means, standard deviations, and median and interquartile ranges for continuous parameters, as well as percentages and frequencies for categorical parameters will be presented. To adjust for intracluster correlation, a generalized linear mixed model with binary outcome will be used to compare the primary outcome (diagnostic yield) between the comparator groups. Additional comparisons between groups will be made using either generalized linear mixed model.

Subgroup analysis will be performed for the following subgroups

- Nodule size: <1.5cm, 1.5-3cm, >3cm
- Presence of bronchus sign
- Solid vs subsolid nodule
- Peripheral vs central location Peripheral defined as outer 1/3 of chest

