Patients who are undergoing a navigational bronchoscopy for biopsy of a peripheral lung lesion and are ≥ 18 years of age at the time of the procedure will be included in this study. Patients will be excluded if they are enrolled in a different study requiring use of one of these specific platforms or if they decline to participate.

Study Design:

This is a single center, open label, pragmatic, non-inferiority, cluster randomized controlled trial comparing clinical outcomes between patients assigned to receive a diagnostic bronchoscopy with either the IonTM Endoluminal System (SSCB) or the ILLUMISITETM Platform (EMN) platform.

Randomization:

Operating rooms are set up each morning with one of the two devices for the day's of prescheduled procedures. Cluster randomization will be used for this study given impracticability of patient-level 1:1 parallel randomization in these circumstances. The ILLUMISITETM Platform (EMN) and IonTM Endoluminal System (SSCB) will be randomly allocated to our two operating rooms each day. All patients undergoing a navigational bronchoscopy will have their procedure performed with the platform assigned to their operating room for the day. A biostatistician not involved in patient care will generate the randomization sequence. Random permuted blocks may be used to ensure balanced cluster allocation. A bronchoscopy scheduler with no knowledge of the allocation scheme will schedule each patient into one of the two operating rooms. Allocations will be concealed in sealed envelopes which will be opened every morning by the operating room staff preparing the rooms.

Sample Size Considerations:

The study team performs 1-4 guided bronchoscopies per day (average of 2 per day) and approximately 400 per year. Based on data from prior studies and the study team's published data, we estimated the diagnostic yield of EMN to be 80%. The diagnostic yield of SSCB has not been fully elucidated, but published data suggest an overall diagnostic yield of 80% as well. Assuming the diagnostic yield for the ILLUMISITE[™] Platform (EMN) is 80%, with a non-

Statistical analysis plan for Robotic versus Electromagnetic Bronchoscopy for Pulmonary LesIon AssessmeNT: the RELIANT trial

PI: [name]

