inferiority margin set at 10%, cluster size of 2, and no intracluster correlation, we need 202 clusters (operating days) to have an 80% power to conclude noninferiority at a one-sided type I error rate of 5%, which corresponds to a target of 425 subjects to reach 202 per arm. The noninferiority margin has been chosen based on what would be considered a clinically significant difference (or, put differently, a difference which might influence a hospital to purchase one platform over the other). In case our average cluster size does not reach 2, we will plan to increase the number of clusters to meet our target enrollment of 425 subjects to reach 202 per arm.

Interventions

All patients meeting the eligibility criteria for this study will be enrolled. Cluster randomization will be used, and patients will be assigned to one of the two comparator arms:

a) IonTM Endoluminal System (SSCB)

b) ILLUMISITE[™] Platform (EMN)

Outcomes

Primary Outcome

The primary endpoint will be diagnostic yield, defined as the proportion of procedures that results in acquisition of lesional tissue.

Lesional tissue is defined by the presence of pathological findings that readily explain the presence of a pulmonary lesion. The following common pathological findings are pre-specified:

- Malignancy
- Specific benign pathologic finding including
 - Organizing pneumonia
 - Frank purulence/robust neutrophilic inflammation
 - o Granulomatous inflammation
 - Other specific benign findings such as hamartoma, amyloidoma or other uncommon causes of PPLs with distinctive pathological patterns.

Biopsies not meeting any of the above lesional pathological criteria will be adjudicated as not meeting the primary outcome (not being "diagnostic"), including biopsies with normal lung parenchyma or airway components on biopsy, atypia not diagnostic of malignancy, or non-specific inflammation. A blinded panel will review all non-malignant biopsies at the end of accrual to confirm specific benign or non-diagnostic findings on biopsy. Procedures will be adjudicated as not meeting the primary outcome if the procedure starts but biopsies are not obtained (due to failure to navigate to the lesion, or complication, or equipment failure). A procedure will be considered started at induction of general anesthesia.

Statistical analysis plan for Robotic versus Electromagnetic Bronchoscopy for Pulmonary LesIon AssessmeNT: the RELIANT trial PI: [name]

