The primary analysis for the trial will use an intent-to-treat approach. Participants will be evaluated by treatment group as assigned regardless of what was delivered. All eligible participants will be included.

The primary outcome variable (diagnostic yield) will be compared between groups using a generalized linear mixed model with one-sided test. The primary model will be covariate adjusted, including fixed effects for device assignment, lesion size, density, peripheral location, and bronchus sign, and a random effect for operator. Should the model demonstrate signs of overfitting, covariates may be selected based on priority order (device assignment, lesion size, density, peripheral location, sign, operator).

If non-inferiority is demonstrated, we will proceed with a superiority analysis using the same approach as the non-inferiority analysis, an adjusted generalized linear mixed effects model with the same covariates used in the primary analysis. No adjustment will be made for multiplicity. The superiority analysis would be conducted at a one sided p-value of 0.05.

Secondary and exploratory analysis

A sensitivity analysis using a *per protocol* approach will be conducted to analyze participants based on the device used. We will use the same approach as the primary analysis, an adjusted generalized linear mixed effects model using the same covariates.

The secondary outcome, procedure duration, will be compared between study groups using a linear mixed model. If the procedure duration is skewed, alternative models may be pursued,

Statistical analysis plan for **R**obotic versus Electromagnetic Bronchoscopy for Pulmonary LesIon AssessmeNT: the RELIANT trial PI: [name] such as a cox regression. The primary model will be covariate adjusted following a similar approach to the analysis of the primary outcome. Analysis of the exploratory endpoints will follow a similar approach.

Safety analysis

Procedure complications are expected in usual care, although uncommon. We will report all procedure complications for each device, overall and by type. If event rates exceed 5%, we may proceed with a comparative analysis, which will involve a generalized linear mixed regression model for binary outcomes as specified for the main analysis, with the exception that covariate adjustment may not be possible. The safety analysis dataset will group participants by device used, regardless of assignment.

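### The SAP primary model has no term or robust variance for the randomised OR-day cluster, so it does not deliver the clustering adjustment the protocol states

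*SAP*

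**What the plan says.** Randomisation is by room and day. Protocol, General Study Design: "The platform set up in each of our two operating rooms will be randomly allocated each morning". SAP, Randomization, says the platforms "will be randomly allocated to our two operating rooms each day".

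Protocol, Statistical Analysis Plan, gives the purpose of the model: "To adjust for intracluster correlation, a generalized linear mixed model with binary outcome will be used to compare the primary outcome". It does not name the level of the random effect.

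SAP, Primary analysis, lists the terms of that model, "including fixed effects for device assignment, lesion size, density, peripheral location, and bronchus sign, and a random effect for operator". If the model appears overfitted, "covariates may be selected based on priority order (device assignment, lesion size, density, peripheral location, sign, operator". No OR-day, room or day term, GEE or robust variance appears anywhere in the SAP. The superiority and per-protocol analyses reuse this model. The duration and exploratory analyses follow a similar approach, and any comparative safety model is specified as for the main analysis.

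The documents name the cluster differently. Protocol, Sample Size Calculation: "we need 202 clusters (OR-days) to have an 80% power to conclude noninferiority". SAP, Sample Size Considerations: "we need 202 clusters (operating days) to have an 80% power to conclude noninferiority". With two rooms in use these are different units. Both assume a cluster size of 2 and zero intracluster correlation. On volume, the SAP says: "The study team performs 1-4 guided bronchoscopies per day (average of 2 per day) and approximately 400 per year".

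**The concern.** In a cluster-randomised trial the variance of the treatment comparison depends on how outcomes correlate within the randomised unit. An analyst who follows the SAP exactly fits a model with no representation of that unit. The one random effect it has, operator, describes something else, and the overfitting rule could remove even that.

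At stake is the confirmatory test. If correlation is specific to a room on a day, an analysis that ignores it tends to understate the variance, and the one-sided 5% error is exceeded. If correlation is shared by both rooms on a day and both rooms have cases, the arms are partly paired, and the same analysis tends to be conservative. The superiority test, also at one-sided 5%, inherits the problem. An analyst who instead tries to honour the protocol must choose a cluster term that the SAP does not specify.

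**Working it through.** **The plan's own figure.** Inputs from Protocol, Sample Size Calculation and the table after it: yields 80% and 80%, margin 10 points, 202 per arm, one-sided alpha 0.05, ICC 0. The Farrington-Manning constrained estimates at the margin are 0.7411 and 0.8411.
- Null SE = sqrt((0.7411 x 0.2589 + 0.8411 x 0.1589)/202) = 0.0401.
- Alternative SE = sqrt(2 x 0.16/202) = 0.0398.
- Power = Phi((0.10 - 1.645 x 0.0401)/0.0398) = 0.803, against 0.80327 in the table.

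The sample size is correct on its inputs. The gap is in the analysis model.

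**Effect of ignoring the cluster.** Let n1 and n2 be the cases in the two rooms on a day, r the room-specific part of the ICC and d the part shared by day. Relative to the independence variance, the true variance is multiplied by

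VF = 1 + {(r + d) E[n1(n1-1) + n2(n2-1)] - 2d E[n1 n2]} / E[n1 + n2],

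and the actual one-sided error is 1 - Phi(1.645/sqrt(VF)).

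The SAP gives 1 to 4 cases a day, average 2. The spread is my assumption: 1, 2, 3, 4 cases with probability 0.35, 0.40, 0.15, 0.10. The mean is 0.35 + 0.80 + 0.45 + 0.40 = 2.0, and E[n(n-1)] = 0.40 x 2 + 0.15 x 6 + 0.10 x 12 = 2.9. The ICCs are also assumed.
- Random split: within-room and between-room terms are each 2.9/2 = 1.45, so VF = 1 + (1.45(r + d) - 1.45d)/2 = 1 + 0.725r.
- Most even split: within 0.7, between 2.2, so VF = 1 + 0.35r - 0.75d.
- All in one room: VF = 1 + (2.9/2)(r + d) = 1 + 1.45(r + d).
- Two per OR-day in both rooms (the planning cluster size, but 4 cases a day): VF = 1 + r - d.

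Example: random split, r = 0.10. VF = 1.0725, square root 1.0356, 1.645/1.0356 = 1.588, error 5.6%.

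| Layout of a day's cases | Correlation | ICC 0.05 | ICC 0.10 | ICC 0.20 |
|---|---|---|---|---|
| Average 2 a day, random split | room-specific | 5.3% | 5.6% | 6.2% |
| Average 2 a day, random split | shared by day | 5.0% | 5.0% | 5.0% |
| Average 2 a day, most even split | room-specific | 5.1% | 5.3% | 5.6% |
| Average 2 a day, most even split | shared by day | 4.7% | 4.4% | 3.7% |
| Average 2 a day, all in one room (upper bound) | either | 5.6% | 6.2% | 7.4% |
| Two per OR-day, both rooms | room-specific | 5.4% | 5.8% | 6.7% |
| Two per OR-day, both rooms | shared by day | 4.6% | 4.1% | 3.3% |

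**Power in the last row.** With SE0 = 0.0398 and true yields 80% and 80%:
- unadjusted, Phi((0.10/SE0 - 1.645)/sqrt(VF)) = 81.3%, 82.0%, 83.4%;
- day-clustered, Phi(0.10/(SE0 sqrt(VF)) - 1.645) = 82.5%, 84.2%, 87.8%.

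**Simulation check.** With 40,000 replicates per setting, yields 0.70 and 0.80, an unadjusted risk-difference z-test and the random split, ICCs of about 0.05, 0.11 and 0.21 gave 5.4%, 5.7% and 6.2% room-specific and 5.0-5.1% shared. Day-clustered variance gave 4.9-5.7% over all simulated settings. Monte Carlo error is about 0.2 points.

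**The case against.** **The effect is small at the documented volume.** This stands. With a random room split the error is 5.3% and 5.6% at ICCs of 0.05 and 0.10, or 5.0% if correlation is shared by day. Errors above 6% need an assumed ICC of 0.20, or all of a day's cases in one room at an ICC of 0.10 or more.

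**The figures are not for the planned test.** This also stands. The SAP adjusts for lesion features and operator, and how much of the correlation those terms absorb is not established.

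**The SAP does model correlation, through operator.** This stands only in part. The protocol names no level for the random effect, operator may overlap with OR-day, and dropping it is conditional. But neither document says that one operator keeps a room all day. Protocol, Assessment of Resource(s), describes about three attending operators and a fellow, against 202 planned clusters. An effect common to all of an operator's days cannot represent one room on one day.

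**The ICC is taken as zero.** That is a sample-size input. Neither document supports it with data or offers it as a reason to leave the cluster out of the analysis, and the protocol commits to adjusting regardless.

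A reader might also infer that the documents identify a cause of room-day correlation, since platforms are set up and calibrated, stay in the room all day, and equipment failure counts as non-diagnostic. The documents do not make that link. They describe set-up to justify cluster randomisation, and they give no failure frequency.

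**Conclusion.** The omission is certain: the SAP as written does not provide the adjustment that the protocol states, and the error rate of the non-inferiority test is not protected if outcomes correlate within an OR-day. The consequence is uncertain in size and direction and probably modest. The illustrative figures rest on assumed ICCs, an assumed spread of daily counts, assumed room splits and an unadjusted test.

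Two stronger readings go too far. A reader might conclude that the planned standard errors are wrong. The documents do not show this: with a random split and correlation shared by day, VF is 1 and the unadjusted variance is right. A reader might also conclude that the trial would be underpowered where the test is conservative. In the calculated case, power stays above the planned 80% and is lower only than day-clustered variance would give.

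Severity is minor to should-fix. It merits action because this is the confirmatory test and the correction is cheap.

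**What to change.** In the SAP, make the primary, superiority, per-protocol and secondary models account for the randomised cluster, and name one of these as primary:

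1. Keep the mixed model with its covariates and operator, and add an OR-day random intercept, with a day intercept as well if it can be estimated.
2. Use variance clustered by calendar day, with operator as a fixed effect, and state that the device effect is then marginal. Day clustering covers both correlation within a room-day and the same-day pairing of the arms. Operator has to move to a fixed effect because operators work across days: a day-clustered sandwich does not sit properly on a model with a random operator effect, and GEE cannot keep one.

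State that the clustering adjustment is exempt from the overfitting rule, and use one definition of the cluster in both documents.

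The cost is SAP wording and a little more analysis work. Room and date are known from the daily allocation and need only be carried into the analysis dataset. Intervals may be slightly wider or narrower. Enrolment and conduct do not change.

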Scheduling the EMN and SSCB systems into each room in advance to allow patients to be scheduled into these rooms based on their randomized allocation appears superficially feasible but would result in procedures being delayed days to weeks potentially, as we do not always have multiple slots available for peripheral pulmonary lesion biopsy on a given day, which is not acceptable from a clinical perspective. Furthermore, we meet a large proportion of our patients the day of the procedure, thus would be unable to enroll and randomize before the day of procedure. When patients are consented for the diagnostic bronchoscopy procedure, eligible patients will then be consented for inclusion in this trial and collection of their data.

Common etiologies of peripheral pulmonary lesions include malignancy and infections, which makes nearly all of these procedures clinically urgent.

These logistical issues have two notable practical consequences:

- 1. Given the set-up time required for these bronchoscopic platforms, they cannot be moved between rooms once set up for the day.
- 2. From the perspective of an individual patient planned to undergo bronchoscopic biopsy of a peripheral pulmonary lesion, it is currently arbitrary whether their biopsy will be performed with EMN or SSCB, which depends on the day they happen to be scheduled and which of our two platforms (EMN and SSCB) happen to be set up in the OR that day. Given no comparative data exists between these two modalities, we have no clinical reason to select patients into one system versus the other. However, the provider retains autonomy to determine the most appropriate course of clinical care based on the presentation of the patient. If new information on treatment practices were to arise and one of our two platforms were recommended for specific cases, the corresponding patients would receive the appropriate treatment and would not be eligible for this study.

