The analysis for the trial will use a intent-to-treat approach. Participants will be evaluated by treatment group as assigned regardless of what was delivered; participants will be excluded if their procedure did not begin, defined as the start of the navigation procedure itself. All eligible participants will be included.

The safety analysis dataset will group participants by device used, regardless of assignment.

Statistical Approach

Our initial analysis will be descriptive in nature, summarizing information that characterizes the cohort and the outcomes. Then, we will proceed with inferential analysis. No interim analyses are planned.

Descriptive Analysis

To characterize the study sample, baseline demographic and clinical data will be described overall and by group. Categorical variables will be described using frequencies and proportions, and continuous variables will be described using means and standard deviations or medians and interquartile ranges, as appropriate. Missingness will be reported for each variable. At a minimum, the following variables will be described at time of enrollment:

- Age (years)
- Gender (male, female, unknown)
- Race (African American, Asian/Pacific Islander, Caucasian, Multiple, Native American, Other, Unknown)
- Ethnicity (Hispanic, Non-Hispanic, Unknown)
- History of cancer (yes/no)
- Smoking History (current, former, never)
- Body mass index (BMI)
- Lesion characteristics
 - o Size (mm)
 - Location (middle vs peripheral)
 - Upper lobe (yes/no)
 - Density (solid, part solid, ground glass opacity)
 - Distance from pleura (cm)
 - Bronchus sign present (yes/no)
- Procedure details

Statistical analysis plan for **R**obotic versus Electromagnetic Bronchoscopy for Pulmonary LesIon AssessmeNT: the RELIANT trial PI: [name]

PI: [name]

- Rapid onsite evaluation (yes/no)
- o Operator
- Digital tomosynthesis (yes/no)
- Cone beam computed tomography (yes/no)
- Biopsy tools

We will describe the outcome variables overall and grouped by study arm using the same approach as for the demographic data. Summary statistics and graphical representations may be displayed, and missingness will be reported for each variable. No statistical comparisons between groups will be done for this descriptive analysis.

Primary analysis

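### The sensitivity analysis labelled 'per protocol' is described as grouping by device used, which is an as-treated analysis, and no per-protocol set is defined

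*SAP*

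**What the plan says.** The SAP, under Primary analysis, sets an intention-to-treat comparison: "Participants will be evaluated by treatment group as assigned regardless of what was delivered". Under Secondary and exploratory analysis it adds one sensitivity analysis, names it per protocol, and says that this "approach will be conducted to analyze participants based on the device used". The model carries over unchanged: "We will use the same approach as the primary analysis, an adjusted generalized linear mixed effects model using the same covariates".

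Nothing else defines the set. The only exclusion under Analysis dataset concerns procedures that never started: "participants will be excluded if their procedure did not begin, defined as the start of the navigation procedure itself". There is no adherence rule, no list of major deviations, and no statement that patients treated with the other platform are left out. The protocol's own Statistical Analysis Plan section names no analysis population.

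The safety set is described in similar terms: "The safety analysis dataset will group participants by device used, regardless of assignment".

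**The concern.** A per-protocol analysis keeps patients in the arm to which they were allocated and leaves out those who did not receive the allocated platform. Grouping by device used moves those patients into the other group. The name and the rule therefore point to different analyses.

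This matters more in a non-inferiority trial than in a superiority trial. Crossover pulls the intention-to-treat difference towards zero, which favours non-inferiority, and readers look to a per-protocol result for reassurance. Here it is the only planned analysis that addresses device non-adherence. If switches depend on how hard the lesion is, regrouping takes a likely failure out of one group and adds it to the other, whereas a per-protocol set only takes it out.

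The protocol leaves some room for patient-dependent switching, since under Informed Consent "the provider retains autonomy to determine the most appropriate course of clinical care based on the presentation of the patient". The SAP also anticipates some non-adherence, because it analyses by assignment whatever was delivered and builds a separate safety grouping.

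**Working it through.** **Inputs from the documents.** EMN yield 80%, SSCB yield 80%, margin 10 points, one-sided alpha 5%, intracluster correlation 0, 202 per arm (Protocol, Sample Size Calculation and the power table that follows it).

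**Assumed inputs.** The documents give no crossover rate and no yield for difficult lesions. I assume 2 to 20 switched cases out of 202, and hard cases with a 50% yield on EMN. At a true difference of 0 the SSCB yield in hard cases is also 50%; at a true -10 points it is 40%.

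**Plan's own figure.** The Farrington-Manning test with restricted estimates 0.741 and 0.841, 202 per arm and alpha 5% gives power 0.80327, exactly as stated. That figure is not in dispute.

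**Step 1: switching unrelated to prognosis.** With a fraction c crossing over in each arm, the intention-to-treat difference is (1 - 2c) × true difference. At a true -10 this is -9.8, -9.6, -9.0 and -8.0 points for c = 1, 2, 5 and 10%. As-treated and per-protocol both return -10.0.

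**Step 2: 10 hard SSCB-assigned cases done with EMN, true difference -10.**
- SSCB patients not switched: (202 × 0.70 - 10 × 0.40) / 192 = 137.4 / 192 = 71.56%.
- EMN arm as assigned: 80.00%.
- EMN users: (202 × 0.80 + 10 × 0.50) / 212 = 166.6 / 212 = 78.58%.
- SSCB arm as assigned: (137.4 + 10 × 0.50) / 202 = 142.4 / 202 = 70.50%.
- As-treated: 71.56 - 78.58 = -7.02.
- Per-protocol: 71.56 - 80.00 = -8.44.
- Intention to treat: 70.50 - 80.00 = -9.50.

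Measured from -10, the as-treated bias is +2.98 and the per-protocol bias +1.56, a ratio of about 1.9. With no true difference the same steps give +2.98, +1.56 and 0.

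**Step 3: the reverse switch, 10 hard EMN-assigned cases done with SSCB, true difference -10.**
- EMN patients not switched: (161.6 - 5) / 192 = 81.56%.
- SSCB users: (141.4 + 10 × 0.40) / 212 = 145.4 / 212 = 68.58%.
- As-treated: 68.58 - 81.56 = -12.98.
- Per-protocol: 70.00 - 81.56 = -11.56.

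The bias has the same size and now works against non-inferiority.

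**Step 4: dependence on the number of switches (SSCB to EMN, true difference 0).**

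| Switched cases | As-treated | Per-protocol | Gap |
|---|---|---|---|
| 2 | +0.6 | +0.3 | 0.3 |
| 4 | +1.2 | +0.6 | 0.6 |
| 10 | +3.0 | +1.6 | 1.4 |
| 20 | +6.0 | +3.3 | 2.7 |

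All these are crude differences, with no covariate adjustment.

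**The case against.** The wording does not say outright that switched patients are regrouped. The safety set is grouped by device used with an explicit disregard of assignment; the sensitivity sentence lacks that phrase and carries the per-protocol name, so dropping switched patients is a possible reading. This stands, but it turns a wrong label into an ambiguous one: two analysts could build different sets, and the text still needs correcting.

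Switching is also constrained. There is one platform of each kind, and once in place "they cannot be moved between rooms once set up for the day". Under Randomization and Blinding, every patient is to have the procedure with the room's platform. Under Protocol Deviations, departures are allowed only to remove an immediate hazard. The sentence after the one on provider autonomy says that patients for whom one platform comes to be recommended would not be eligible, so they would leave the trial and not cross over. This stands: switches may be few, and no rate is given.

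The model adjusts for lesion size, density, peripheral location and bronchus sign. Where switching follows those features, adjustment should remove part of the bias; difficulty that they do not capture would remain.

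A reader might infer that this analysis breaks randomisation where a per-protocol one would not. That is not so, because excluding crossovers also gives up the randomised comparison; the difference is one of degree. A reader might also infer that the analysis cannot check the non-inferiority result. That is too strong: Step 1 shows that it removes dilution as fully as per-protocol when switching is unrelated to prognosis.

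**Conclusion.** The label and the rule disagree, and no per-protocol set exists. On the natural reading the planned analysis is as-treated. Under selective switching it carries about twice the bias of a per-protocol set, towards or against non-inferiority according to the direction of the switches. At 10 assumed hard cases the gap between the two is about 1.4 points; at 2 to 4 cases it is 0.3 to 0.6 points. These sizes rest on an assumed 50% hard-case yield, assumed counts, every switch going one way, and no covariate adjustment.

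One might be tempted to read the 3-point shift as inflating the trial's type I error. At the margin, a crude as-treated comparison shifted by 3 points would reject about 18% of the time instead of 5%. By the same method a per-protocol set would reject about 10% of the time and intention to treat about 6%. The documents do not support calling the 18% the trial's error rate, because the conclusion comes from the intention-to-treat test, which the definition of this analysis leaves untouched. It is a minor correction.

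**What to change.** Define the per-protocol set as eligible participants whose procedure started and was done with the assigned platform, analysed in the assigned arm with the primary model. Use the same definition of procedure start as the primary analysis set. Keep the device-used analysis if wanted, under the name 'as-treated' and as supplementary. Report the number of crossovers by arm, with reasons, so that a reader can judge whether switching was rare or selective. Settle the definition before crossovers are known by arm, so that the choice is not post hoc.

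The cost is a few sentences in the SAP, one extra model run and a slightly smaller set for that run. Sample size and trial conduct do not change.
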